## **CLINICAL TRIAL PROTOCOL SYNOPSIS**

Company name	Boehringer Ingelheim
Protocol date	15 May 2019
Revision date	13 February 2020
BI trial number	1386-0016
Title of trial	A phase I parallel group study in healthy subjects to evaluate the effect of multiple oral doses of BI 1467335 and phenelzine as positive control on blood pressure response to oral tyramine (double-blind, randomised, placebo-controlled design for BI 1467335 treatment groups, open label for phenelzine)
Principal Investigator:	[REDACTED]
Trial site	[REDACTED]
Clinical phase	I
Trial rationale	
In-vitro tests revealed a reversible inhibition of MAO-A catalyzed kynuramine deamination by BI 1467335. The reversible inhibition of MAO-A was considered to be probably of remote clinical relevance, which nevertheless requires further clinical evaluation. Therefore, as long as no clinical data are available, in ongoing clinical studies with BI 1467335 it is recommended that as a precautionary measure subjects should refrain from tyramine-rich food while on treatment.
 
Study 1386-0016 will be conducted to confirm that multiple doses of BI 1467335 at therapeutic dose levels do not inhibit MAO-A activity in humans thus justifying to lift dietary restrictions.

Trial objective	To investigate the effect of escalating doses of oral tyramine on systolic blood pressure (SBP) at baseline and following an oral treatment with BI 1467335 up to 39 days at a dose of 10 mg or 15 mg once daily compared to placebo and phenelzine as positive control.
Trial design	
Double-blind, randomised, multiple-dose, placebo- controlled within BI 1467335 dose groups, parallel group design.
 
Open label for phenelzine treatment group (positive control without placebo control).
 
BI 1467335 dose groups will not start before at least 8 subjects of the phenelzine treatment group have completed the trial.

Proprietary confidential information © 2020 Boehringer Ingelheim International GmbH or one or more of its affiliated companies

Trial endpoints:	
Primary endpoint: Tyramine sensitivity factor (TSF), defined as ratio of the tyramine dose causing an increase of systolic blood pressure (SBP) <math>\geq 30</math> mmHg for at least 3 consecutive measurements (TYR30) at baseline and at steady state following multiple oral doses of BI 1467335, placebo or phenelzine.
 
Secondary endpoints: Not applicable.

Number of subjects total entered each treatment	62 Dose Group 1 (BI 1467335 - 10 mg): 24 subjects (16 active + 8 placebo); Dose Group 2 (BI 1467335 - 15 mg): 24 subjects (16 active + 8 placebo); Dose Group 3 (phenelzine - 30 mg): 14 subjects (all active).
Diagnosis	Not applicable
Main criteria for inclusion	Healthy male/female subjects, age of 18 to 45 years (inclusive), body mass index (BMI) of 18.5 to 29.9 kg/m  (inclusive); at least 30% of each gender to be included into each Dose Group
Test product dose mode of admin.	BI 1467335, film-coated tablets, 5 mg of free base 10 mg (2 x 5 mg) QD and 15 mg (3 x 5 mg) QD Oral with 240 mL of water
Reference product dose mode of admin.	Matching placebo to BI 1467335 Not applicable Oral with 240 mL of water
Comparator dose mode of admin.	Phenelzine (Nardil ® ), tablets, 15 mg 15 mg BID Oral with 240 mL of water

Proprietary confidential information © 2020 Boehringer Ingelheim International GmbH or one or more of its affiliated companies

Challenge agent	Tyramine powder in capsules
dose	Baseline (Day -10 to Day -1, tyramine powder alone; each subject receives escalating doses, dose escalation to be stopped as soon as TYR30 has been obtained): 10, 25, 50, 100, 200, 300, 400, 500, 600, and 700 mg QD.  At steady state (for BI 1467335 dose groups Day 29 up to Day 39 , for phenelzine dose group Day 8 to Day 19, tyramine powder in combination with assigned study treatment; tyramine dose escalation to be stopped as soon as TYR30 has been obtained): 5, 10, 25, 50, 100, 200, 300, 400, 500, 600, and 700 mg QD An intermediate dose of 150 mg QD only in phenelzine group.
mode of admin.	Oral with 240 mL of water
Duration of treatment	Baseline tyramine challenge up to 10 days (Day -10 to Day -1), tyramine challenge to be stopped individually as soon as baseline TYR30 has been established.  BI 1467335 or placebo will be administered from Day 1 up to Day 39 (treatment will be stopped as soon as individual TYR30 on treatment with BI 1467335 has been attained).  Phenelzine will be administered from Day 1 up to Day 19 (treatment will be stopped as soon as individual TYR30 on treatment with phenelzine has been attained).  From Day 8 (phenelzine) or Day 29 (BI 1467335 or placebo) onwards, tyramine challenge up to 12 days (Day 8 to Day 19 for phenelzine or Day 29 to Day 39 for BI 1467335 or placebo) concomitantly to the study medication.
Statistical methods	The primary endpoint tyramine sensitivity factor (ratio of TYR30 at steady state compared to TYR30 at baseline; TSF) will be compared between the different treatment arms (BI 1467335 10mg, 15mg, Placebo and Phenelzine).  The statistical model used will be an analysis of variance (ANOVA) model on the logarithmic scale including treatment as fixed effect.  Descriptive statistics for the primary endpoint TSF will be calculated.

Proprietary confidential information © 2020 Boehringer Ingelheim International GmbH or one or more of its affiliated companies

## FLOW CHART (BI 1467335 OR PLACEBO)

Visit	Day	Planned time (relative to first drug administration) [h:min]	Approximate clock time of actual day [h:min]	Event and comment	Safety laboratory	12-lead ECG	Monitoring of BP 	Vital signs (BP, PR)	Questioning for AEs and concomitant therapy 
1	-31 to -13			Screening (SCR) 	x				
2	-12		14:00	Admission to trial site	x 	x	x		
	-11		06:00		x 	x 		x 	
			07:25						▲
			08:00	First tyramine administration 					
			08:30						
			09:00						
			10:00						
			12:00	Lunch 		x			
			16:00					x	
	-10 to -2		06:00			x 		x 	
			07:25						▲
			08:00	Tyramine administration 					
			08:30						
			09:00						
			10:00						
			12:00	Lunch  , discharge from trial site as soon as TYR30 achieved		x			
			16:00					x	
3	-1	-18:00	14:00	Admission to trial site	x 				x
	1	-0:30	07:30	Allocation to treatment	x 	x 	x 	x 	
		0:00	08:00	First drug administration, discharge from trial site					
	2	24:00	08:00	Drug administration 					
	3	48:00	08:00	Drug administration 					
	4	72:00	08:00	Drug administration 					
	5	96:00	08:00	Drug administration 					
	6	120:00	08:00	Drug administration 					
		126:00	14:00	Admission to trial site	x 				x
	7	144:00	08:00	Drug administration Dispense of study medication Discharge		x 	x 	x 	
	8	168:00	08:00	Drug administration 					
	9	192:00	08:00	Drug administration 					
	10	216:00	08:00	Drug administration 					
	11	240:00	08:00	Drug administration 					
	12	264:00	08:00	Drug administration 					
	13	288:00	08:00	Drug administration 					
		294:00	14:00	Admission to trial site	x 				x

Proprietary confidential information © 2020 Boehringer Ingelheim International GmbH or one or more of its affiliated companies

Visit	Day	Planned time (relative to first drug administration) [h:min]	Approximate clock time of actual day [h:min]	Event and comment	Safety laboratory	12-lead ECG	Monitoring of BP 	Vital signs (BP, PR)	Questioning for AEs and concomitant therapy 
3	14	312:00	08:00	Drug administration Dispense of study medication Discharge	x 	x 		x 	x 
	15	336:00	08:00	Drug administration 					
	16	360:00	08:00	Drug administration 					
	17	384:00	08:00	Drug administration 					
	18	408:00	08:00	Drug administration 					
	19	432:00	08:00	Drug administration 					
	20	456:00	08:00	Drug administration 					
		462:00	14:00	Admission to trial site	x 				x
	21	480:00	08:00	Drug administration Dispense of study medication Discharge		x 		x 	x 
	22	504:00	08:00	Drug administration 					
	23	528:00	08:00	Drug administration 					
	24	552:00	08:00	Drug administration 					
	25	576:00	08:00	Drug administration 					
		582:00	14:00	Admission to trial site Start of hospitalisation	x 				x
	26	600:00	08:00	Drug administration					
	27	624:00	08:00	Drug administration					
	28	648:00	08:00	Drug administration	x 	x 		x 	x 
		648:30	08:30						
		650:00	10:00	Light breakfast 					
		652:00	12:00	Lunch 					
		656:00	16:00	Snack (voluntary) 					
		658:00	18:00	Dinner 					
		660:00	20:00					x	x
	29-39	670:00 - 920:00	06:00			x 			x 
			07:25				▲		
			08:00	Drug + tyramine administration 					
			08:30			x		x	
			09:00					x	
			10:00			x		x	
			12:00	Lunch  , discharge from trial site as soon as TYR30 achieved		x	▼		x
			16:00	Snack (voluntary) 				x	
4	41 to 51			End of trial (EoTrial) examination 	x	x		x	x

1. Subject must be informed and written informed consent obtained prior to starting any screening procedures. Screening procedures include physical examination, check of vital signs, ECG, safety laboratory (including drug screening and pregnancy test in females), demographics (including determination of body height and weight, smoking status and alcohol history), relevant medical history, concomitant therapy and review of inclusion/exclusion criteria.

Proprietary confidential information © 2020 Boehringer Ingelheim International GmbH or one or more of its affiliated companies

2. The time is approximate; the procedure is to be performed and completed within the 3 h prior to drug administration.
3. If several actions are indicated at the same time, the intake of meals will be the last action.
4. At the end of trial visit the EoTrial examination includes physical examination, body weight, vital signs, ECG, safety laboratory (including pregnancy test in females), recording of AEs and concomitant therapies.
5. Only drug and alcohol screening in urine will be done at this time.
6. AEs and concomitant therapies will be recorded throughout the trial, but will be specifically asked for at the times indicated in the [Flow Chart](#) above.
7. From Day -11 to Day -2 escalating oral doses of tyramine from 10 to 700 mg /day will be administered. Baseline blood pressure prior to tyramine dosing defined as three consecutive measurements with a maximum range of 10 mmHg or, if a stable SBP will not be obtained within the 35 minutes, the mean of all 7 readings. Blood pressure monitoring continues 5 minutes after tyramine administration and approximately every 5 minutes thereafter for at least 2 hours and then approximately every 15 minutes for an additional 2 hours. Tyramine dose escalation is to be terminated when the predefined target elevation in SBP is reached (i.e., SBP increased  $\geq$ 30 mmHg from baseline for three consecutive measurements). Participants who do not attain the predefined target elevation in SBP within 4 hours after the maximum tyramine dose (700 mg) on Day -2 or TYR30 is  $<$  200 mg are screening failures. All other participants are going to be included in the study.
8. From Day 29 to Day 39 escalating oral doses of tyramine from 5 to 700 mg /day will be administered in Dose Groups 1 and 2 (concomitantly with BI 1467335 or placebo). The treatment is to be terminated once the participant reaches the predefined target elevation in SBP (i.e., SBP increased  $\geq$ 30 mmHg from baseline for 3 consecutive measurements), and then the participant is allowed for discharge after an overnight stay at trial site.
9. On Days 2 to 6, 8 to 13, 15 to 20 and 22 to 25, subjects are allowed to take their study medication at home if deemed appropriate by the investigator. Compliance of medication intake will be monitored by subject diary and daily phone contact (e.g. text message) between subject and site. The scheduled time for drug intake throughout the study for subjects assigned to Dose Group 1 and 2 (BI 1467335 or placebo) is 08:00 (applies for intake at home and at the trial site).
10. A pharmacogenomic sample will be collected (see [Section 5.6.2](#)). If not possible at V3, this sample may also be collected during a later visit.

13. This sample to be taken directly prior to dosing of BI 1467335 or placebo.

Proprietary confidential information © 2020 Boehringer Ingelheim International GmbH or one or more of its affiliated companies

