4	21 to 31			End of trial (EoTrial) examination 	x	x		x	x

1. Subject must be informed and written informed consent obtained prior to starting any screening procedures. Screening procedures include physical examination, check of vital signs, ECG, safety laboratory (including drug screening and pregnancy test in females), demographics (including determination of body height and weight, smoking status and alcohol history), relevant medical history, concomitant therapy and review of inclusion/exclusion criteria. .
2. The time is approximate; the procedure is to be performed and completed within the 3 h prior to drug administration.
3. If several actions are indicated at the same time, the intake of meals will be the last action.
4. At the end of trial visit the EoTrial examination includes physical examination, body weight, vital signs, ECG, safety laboratory (including pregnancy test), recording of AEs and concomitant therapies.
5. Only drug and alcohol in urine screening will be done at this time.
6. AEs and concomitant therapies will be recorded throughout the trial, but will be specifically asked for at the times indicated in the [Flow Chart](#) above.
7. From Day -11 to Day -2 escalating oral doses of tyramine from 10 mg to 700 mg /day will be administered. Baseline blood pressure prior to tyramine dosing defined as three consecutive measurements with a maximum range of 10 mmHg or, if a stable SBP will not be obtained within the 35 minutes, the mean of all 7 readings. Blood pressure monitoring continues 5 minutes after tyramine administration and approximately every 5 minutes thereafter for at least 2 hours and then approximately every 15 minutes for an additional 2 hours. Tyramine dose escalation is to be terminated when the predefined target elevation in SBP is reached (i.e., SBP increased  $\geq$ 30 mmHg from baseline for three consecutive measurements). Participants who do not attain the predefined target elevation in SBP within 4 hours after the maximum tyramine dose (700 mg) on Day -2 are screening failures. All other participants are going to be included in the study.

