### 3. DESCRIPTION OF DESIGN AND TRIAL POPULATION

### 3.1 OVERALL TRIAL DESIGN AND PLAN

In total, 62 healthy male and female subjects are planned to participate in this multiple dose study.

The primary outcome of the study will be the tyramine sensitivity factor (TSF), which is defined as the ratio of the tyramine dose causing an increase in systolic blood pressure (SBP)  $\geq 30$  mmHg for at least 3 consecutive measurements (TYR30) at baseline and following a treatment of 28 days with BI 1467335 or placebo QD, or 7 days with phenelzine BID. A treatment duration of 28 days is required for BI 1467335 to reach steady state, whereas 7 days is considered sufficient for phenelzine.

As part of the screening procedure subjects will be challenged with escalating oral doses of tyramine. Tyramine doses will be escalated from 10 mg to 700 mg QD (25, 50, 100, 200, 300, 400, 500, 600, 700 mg) on a daily basis. For each subject, the tyramine dose escalation will be stopped when an increase of systolic blood pressure (SBP)  $\geq 30$  mmHg for at least 3 consecutive measurements is measured (i.e. TYR30). Participants who will not attain the predefined target elevation in SBP within 4 hours after the highest tyramine dose (700 mg) will not be included in the study.

Subjects considered eligible to enter the study will be assigned to one of three dose groups. The three dose groups to be evaluated are outlined in [Table 3.1: 1](#).

Table 3.1: 1 Dose groups

Dose Group	1	2	3
	BI 1467335	BI 1467335	Phenelzine (Nardil®)
Daily dose (mg)	10	15	30
Posology	1-0-0	1-0-0	1-0-1
Treatment duration	Up to Day 39	Up to Day 39	Up to Day 19
Number of subjects	24	24	14
Subjects receiving placebo	8	8	0
Subjects receiving active drug	16	16	14

Dose Group 1 and 2 consists of 24 subjects each, with 16 subjects per dose group assigned to BI 1467335 (active drug) and 8 subjects assigned to placebo. Both BI 1467335 dose groups will be conducted according to a double-blind, randomised, multiple-dose, placebo-controlled within dose groups, parallel group design.

Dose Group 3 will be conducted open-label with no placebo control, and consists of 14 subjects receiving the same treatment of phenelzine as positive control (comparator).

Proprietary confidential information © 2020 Boehringer Ingelheim International GmbH or one or more of its affiliated companies

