18. Intention to perform excessive physical activities within one week prior to the administration of trial medication or during the trial
19. Inability to comply with the dietary regimen of the trial site
20. A marked baseline prolongation of QT/QTc interval (such as QTc intervals that are repeatedly greater than 450 ms in males or repeatedly greater than 470 ms in females) or any other relevant ECG finding at screening
21. A history of additional risk factors for *Torsade de Pointes* (such as heart failure, hypokalaemia, or family history of Long QT Syndrome)
22. Subject is assessed as unsuitable for inclusion by the investigator, for instance, because the subject is not considered able to understand and comply with study requirements, or has a condition that would not allow safe participation in the study
23. Use of MAO inhibitors within 90 days before tyramine dosing
24. Use of fluoxetine within 5 weeks before tyramine dosing
25. Use of over-the-counter sympathomimetic or grapefruit products within 7 days before tyramine dosing
26. Subject has a known intolerance to tyramine-containing foods
27. At screening, no increase of systolic blood pressure > 30 mmHg during tyramine challenge at the highest tested dose of 700 mg tyramine

Proprietary confidential information © 2020 Boehringer Ingelheim International GmbH or one or more of its affiliated companies

Female subjects will not be allowed to participate, if any of the following apply:

28. Positive pregnancy test, pregnancy, or plans to become pregnant within 30 days after study completion
29. Lactation

For study restrictions, refer to [Section 4.2.2](#).

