## 7. STATISTICAL METHODS AND DETERMINATION OF SAMPLE SIZE

### 7.1 STATISTICAL DESIGN – MODEL

The main objective of this trial is to compare the primary endpoint tyramine sensitivity factor (ratio of TYR30 at steady state compared to TYR30 at baseline) as listed in [Section 2.1.2](#) between the different treatment arms (BI 1467335 10mg, 15mg, Placebo and Phenelzine).

The trial will be evaluated statistically by use of a linear model for the logarithmically transformed endpoint.

The assessment of safety and tolerability is a further objective of this trial, and will be evaluated by descriptive statistics for the parameters specified in [Section 2.2.2.2](#).

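### A 200 mg lower limit on baseline TYR30 stands in the BI 1467335/placebo flow chart only, so placebo and phenelzine may be selected differently on a component of TSF

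*Protocol*

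**What the plan says.** The entry rule on baseline TYR30 appears in five places in the protocol.

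- **Flow chart, BI 1467335 or placebo, footnote 7.** Two conditions: no TYR30 by 700 mg is a failure, and subjects with TYR30 below "200 mg are screening failures".
- **Flow chart, phenelzine, footnote 7.** One condition only, non-attainment "after the maximum tyramine dose (700 mg) on Day -2 are screening failures. All other participants are going to be included in the study".
- **Section 3.1, all groups.** Only subjects who miss the target "within 4 hours after the highest tyramine dose (700 mg) will not be included in the study".
- **Section 3.3.3, exclusion 27, all groups.** Only "no increase of systolic blood pressure > 30 mmHg during tyramine challenge at the highest tested dose of 700 mg tyramine".
- **Section 5.6.1, all groups.** The same single 700 mg rule as Section 3.1.

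No amendment entry in Section 11 and no part of the SAP mentions a 200 mg limit or a reason for treating the groups differently.

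On the analysis, Section 7.1 takes TSF as the "ratio of TYR30 at steady state compared to TYR30 at baseline". C/R is one of the planned ratios of geometric means with a 90% confidence interval (Sections 7.2 and 7.3.1). SAP 7.4.1 fits T1, C and R in one ANOVA on log TSF with treatment as the only effect. Phenelzine is open label and not randomised (Sections 4.1.5 and 7.6).

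**The concern.** Baseline TYR30 is one of the two quantities that make up TSF. Cutting it off at 200 mg in one arm and not in the other selects the arms differently on part of the outcome. Some low baseline readings are low by chance and would be higher on repeat. Removing them in placebo but keeping them in phenelzine shifts the mean log TSF of one arm relative to the other. A model with treatment as its only term leaves that shift in C/R, and a larger sample would not shrink it. Section 3.2 makes phenelzine the benchmark against which the BI results are read.

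Two practical gaps follow.

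- **Which rule governs a subject.** Subjects are assigned to a dose group after the screening challenge. Once 8 phenelzine subjects have completed, all groups may enter (Section 3.1). For the remaining 14 − 8 = 6 phenelzine places, the documents do not say which flow chart applies to someone not yet assigned.
- **How a breach is handled.** SAP Table 6.2: 1 allows removal from the per protocol set for breaches of the inclusion or exclusion criteria (A1, A2). The 200 mg limit is not among the listed criteria. It is therefore unclear whether a placebo subject at 100 mg stays in the primary analysis.

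**Working it through.** **1. The plan's own precision figure.** Inputs from Section 7.7: gCV 86%, 16 per arm (N = 32), two-sided 90% interval, 95% assurance.

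- σ = √ln(1 + 0.86²) = 0.744
- log half-width = t(0.95; 30) × σ × √(1/16 + 1/16) × √(χ²(0.95; 30)/30) = 1.697 × 0.744 × 0.3536 × √(43.77/30) = 0.539
- precision = exp(0.539) = 1.715, against 1.72 in Table 7.7: 1. At gCV 80% the result is 1.665, against 1.67.

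The table reproduces. For C/R with 14 against 16 subjects the same formula gives 1.76 (28 df), 1.71 (43 df, three arms of 16, 16 and 14) or 1.69 (58 df, four arms).

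**2. Ranges allowed by the flow charts as written.** Baseline TYR30 can be 200 to 700 mg in placebo and 10 to 700 mg in phenelzine.

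**3. Size of the shift.** Let y = ln(baseline TYR30) − ln(steady-state TYR30). When C/R as written is compared with C/R under a common 200 mg rule, the placebo term cancels:

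shift = exp{mean y in phenelzine, no limit − mean y in phenelzine, baseline ≥ 200 mg}

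The documents give no baseline distribution, so these inputs are assumptions:

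- log-normal true thresholds, with between-subject log-SD 0.35 or 0.5
- per-challenge log-SD 0.2 or 0.5
- an 8-fold phenelzine effect
- subjects without TYR30 at steady state set to 700 mg

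The dose grids are the protocol's, and baseline non-attainers at 700 mg are excluded in every arm. Each range covers the four SD settings, with 400,000 simulated subjects per arm.

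| Assumed median | Phenelzine subjects below 200 mg | Placebo TSF under the 200 mg rule (baseline/steady state) | C/R as written ÷ C/R under common rule |
|---|---|---|---|
| 450 mg | 0–2% | 0.93–0.99 | 0.98–1.00 |
| 350 mg | 0–5% | 0.97–1.00 | 0.97–1.00 |
| 250 mg | 1–11% | 1.00–1.05 | 0.93–1.00 |
| 200 mg | 4–17% | 1.02–1.10 | 0.90–0.98 |

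The largest shift in the 250 to 450 mg range takes C/R from 6.64 to 6.21, and 6.21/6.64 = 0.935. At an assumed 150 mg with wider variances (between-subject 0.5 to 0.8, per-challenge 0.3 to 0.53, 6-fold effect) the shift was 6 to 18%.

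**4. Direction.** With TSF as baseline/steady state, C/R exceeds 1 and is multiplied by 0.93 to 1.00. With steady state/baseline, C/R is below 1 and is multiplied by the reciprocal, 1.00 to 1.07. Either way it moves towards 1.

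**5. Against the precision.** ln(0.935) = −0.067, and the log half-width is ln(1.71) = 0.537. The ratio is 0.067/0.537, about one eighth of the half-width.

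**6. Does a covariate repair it?** The selection acts on the observed baseline itself. Conditioning on that baseline therefore removes it, provided that the slope is linear and common to the arms. In the simulations, adding log baseline TYR30 brought C/R to within about 1% of the common-rule value in every setting.

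**The case against.** The strongest reply is that this is a wording slip of little consequence. Three all-group sections and one flow chart agree, and one footnote departs from them. Protocol 6.2.1 already makes the challenge result mandatory for final inclusion. SAP 6.2 requires every deviation to be assessed and lets the deviation table be extended by the Report Planning Meeting. SAP 7.4.2 already summarises baseline TYR30 by treatment, which would show an imbalance. The trial is exploratory with no formal test, and C/R is open label and non-randomised in any case. With 0 to 11% of phenelzine subjects below the limit, at most about 14 × 0.11 = 1.5 people are involved.

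Most of this stands and limits the weight of the point. It does not remove the contradiction, and the deviation process names no 200 mg rule to apply.

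Several stronger readings are tempting but not supported:

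- **That the 200 mg rule pushes placebo TSF above 1.** The 700 mg rule removes high baseline readings in every arm and works the other way. Simulated placebo TSF was 0.93 to 1.05 for medians of 250 to 450 mg.
- **That only placebo and BI show regression to the mean.** Phenelzine is also truncated, at 700 mg.
- **That C/R is known to be biased numerically downwards.** That requires baseline in the numerator. Section 7.1 puts it in the denominator. SAP 5.1 names baseline first, and the statement in Section 3.2 that phenelzine raises TSF also fits baseline/steady state.
- **That the arms were in fact selected differently.** The documents show conflicting instructions, not which one the site followed.

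**Conclusion.** The point holds as an internal contradiction with a small, avoidable effect on one contrast. If the two flow charts are followed, phenelzine and placebo enter under different rules on a component of TSF, and the planned model does not correct C/R. T1/R is unaffected, because both arms share one flow chart.

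The size cannot be computed from the documents. Under assumed median thresholds of 250 to 450 mg the shift in C/R is 0 to 7%, and at 200 mg up to about 10%. It is towards 1 if TSF is baseline/steady state, and by the reciprocal factor if it is steady state/baseline. A reader might infer that the phenelzine benchmark is invalid. It is not: the shift is well inside the planned precision factor of about 1.7 and would not hide a several-fold effect. The contradiction in the text is certain; the magnitude is conditional on the stated assumptions.

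**What to change.** **Protocol wording.** Reconcile Sections 3.1, 3.3.3 and 5.6.1 and both flow charts so that one baseline TYR30 entry rule is stated throughout. The documents do not show which rule was intended, so the sponsor must say. State the direction of TSF once and use it in both documents.

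**Data already collected.**

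- Add log baseline TYR30 as a covariate in the SAP 7.4.1 model, or as a pre-stated sensitivity analysis. The sponsor's trial functions are unblinded (Protocol 4.1.5), so the second avoids any appearance of choosing the primary model after seeing data.
- Report C/R restricted to baseline TYR30 of at least 200 mg in all arms, as a sensitivity analysis.
- List any BI/placebo subject entered below 200 mg for assessment at the Report Planning Meeting.

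**Cost.** Text edits, one residual degree of freedom, one extra model run and one listing. No new data are needed.
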